### 7.5. Assessment of Severity

7.5.1.1. AE severity should be recorded and graded according to the Grading Scale for Severity of Adverse Events and laboratory Abnormalities (Appendix 4). For AE associated with laboratory abnormalities, the event should be graded on the basis of the clinical severity in the context of the underlying conditions; which might not be in agreement with the grading of the laboratory abnormality.

7.5.1.2. The distinction between the seriousness and the severity of an AE should be noted. Severe is a measure of intensity; a severe reaction is not necessarily a serious reaction. For example, a subject might have a headache that is described as severe, but would not be considered a SAE unless it met one of the criteria for serious events.

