#### **7.6.2. Grades 1 and 2 Clinical Event or Laboratory Abnormality**

7.6.2.1. Continue study drug at the discretion of the Investigator

#### **7.6.3. Grade 3 Clinical Event or Laboratory Abnormality**

7.6.3.1. For Grade 3 clinical event or clinically significant laboratory abnormality, study drug may be continued if the event is considered to be unrelated to study drug.

7.6.3.2. For a Grade 3 clinical event or clinically significant laboratory abnormality confirmed by repeat testing that is considered to be related to the study drug, study drug will be withheld until the toxicity returns to  $\leq$  grade 2. When restarting study drug following resolution of the adverse event, the study drug should be restarted at full dose.

7.6.3.3. If following re-challenge with study drug a laboratory abnormality returns to  $\geq$  Grade 3 and is considered to be related to the study drug, then the study drug will be permanently discontinued and the subject managed according to local practice. Recurrence of laboratory abnormalities considered unrelated to the study drug may not require permanent discontinuation.

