#### 8.3.2. Laboratory:

8.3.2.1. This dataset contains all subjects' laboratory data, in the format of one observation per subject per test code per visit per accession number. Here, we derive the study visits according to the study window defined in the SAP, as well as re-grade the laboratory toxicity per protocol. If the laboratory data are collected from multiple local lab centers, this analysis dataset will also centralize the laboratory data and standardize measurement units by using conversion factors.

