## APPENDIX 4 GRADING SCALE FOR SEVERITY OF ADVERSE EVENTS AND LABORATORY ABNORMALITIES

Laboratory Tests	Grade 1	Grade 2	Grade 3	Grade 4
Hemoglobin	8.5-10.0	7.5-8.49	6.5-7.49	<6.5
ANC	1000-1300	750-999	500-749	<500
Platelets	100-125	50-99	25-49	<25
WBC	2.0-2.5	1.5-1.99	1.0-1.49	<1
Hyponatremia	>130	125-129	121-124	<121
Hypernatremia	<150	150-154	154-159	>159
Hypokalemia	>3	2.5-3.0	2.0-2.49	<2.0
Hyperkalemia	5.6-6.0	6.01-6.5	6.51-7.0	>7.0
Hypoglycemia	55-64	40-54.9	30-39.9	<30
Hyperglycemia, Fasting	110-125	126-250	251-500	>500
Hypocalcemia (corrected)	Below normal but above 7.8	7.0-7.8	6.1-6.9	<6.1
Hypercalcemia (corrected)	Above normal but below 11.5	11.5-12.5	12.6-13.5	>13.5
Total Bilirubin	Up to 1.5 x ULN	1.5-2.5 x ULN	2.5-5.0 x ULN	>5.0 x ULN
BUN	1.25-2.5 x ULN	2.6-5.0 x ULN	5.1-10 x ULN	>10 x ULN
Creatinine	1.5-2.0	2.01-3.00	3.01-6.00	>6.00
Bicarb	16-LLN	11-15.9	8-10.9	<8.0
Triglycerides (fasting)	NA	500-750	751-1200	>1200
LDL (fasting)	130-160	161-190	>190	NA
CK	3-6 x ULN	6.1-10 x ULN	10.1-20 ULN	>20 x ULN
AST	1.25-2.5 x ULN	2.6-5.0 x ULN	5.1-10 x ULN	>10 x ULN
ALT	1.25-2.5 x ULN	2.6-5.0 x ULN	5.1-10 x ULN	>10 x ULN
GGT	1.25-2.5 x ULN	2.6-5.0 x ULN	5.1-10 x ULN	>10 x ULN
Alk Phos	1.25-2.5 x ULN	2.6-5.0 x ULN	5.1-10 x ULN	>10 x ULN
Lipase	1.0-1.5 x ULN	1.51-3.0 x ULN	3.01-5.0 x ULN	>5.0 x ULN
Albumin	NA	2.0 to <LLN	<2.0	NA
Hematuria	>ULN-10	>10-75	>75	NA
Proteinuria	1+	2-3+	4+	NA
Glycosuria	1+	2-3+	4+	NA
Cardiac Arrhythmia	Asymptomatic and no intervention indicated	Asymptomatic and non-urgent intervention indicated	Symptomatic and non-urgent intervention indicated	Life threatening or urgent intervention indicated
Cardiac ischemia/infarct	NA	NA	Stable angina or testing with ischemia	Unstable angina or acute MI
Hemorrhage	NA	Symptomatic, no transfusion indicated	Symptomatic, ≤ 2 units PRBC's transfusion indicated	Life threatening or > 2 units PRBC's transfusion indicated
Hypertension	Systolic: 140-159 Diastolic: 90-99	Systolic: 160-179 Diastolic: 100-109	Systolic: >179 Diastolic: 110	Life threatening (i.e. malignant hypertension) or requiring hospital admission
Hypotension	NA	Symptomatic, corrected with oral fluids	Symptomatic, IV fluids indicated	Refractory shock

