## APPENDIX 4: Grading Scale for Severity of Adverse Events and Laboratory Abnormalities

Cognitive and behavior (including dementia and ADD)	Minimal, without impact on activities. No special resources indicated	moderate, with impact on activities or part-time special resources indicated	marked, unable to perform typical activities or full-time special resources indicated	Disabling causing inability to care for self or institutionalization
CNS Ischemia	NA	NA	Transient ischemic attack	CVA/stroke with neurological deficit
Headache	Minimal but detectable on exam, without impact on activities	moderate, with impact on activities	severe, unable to perform typical activities	Disabling causing inability to care for self or hospitalization indicated
Insomnia	NA	moderate, with impact on activities or part-time special resources indicated	marked, unable to perform typical activities or full-time special resources indicated	Disabling causing inability to care for self
Neuromuscular Weakness	Asymptomatic but detectable on exam, without or minimal impact on activities	moderate, with impact on activities	severe, unable to perform typical activities	Disabling causing inability to care for self or respiratory failure
Sensory alteration	Asymptomatic but detectable on exam, without or minimal impact on activities	moderate, with impact on activities	severe, unable to perform typical activities	Disabling causing inability to care for self or respiratory failure
Seizure, new onset	NA	1 seizure	2-4 seizures	Prolonged or repetitive seizures or difficult to control
Seizure, pre-existing	NA	Increased frequency, no change in character	Change from baseline in either duration or quality	Prolonged or repetitive seizures or difficult to control
Syncope (not associated with a procedure)	NA	Present	NA	NA
Vertigo	without impact on activities	moderate, with impact on activities	severe, unable to perform typical activities	Disabling causing inability to care for self or respiratory failure
Arthralgia	without impact on activities	moderate, with impact on activities	severe, unable to perform typical activities	Disabling causing inability to care for self or respiratory failure
Bone Mineral Loss	BMP t-score or z-score -2.5 to -1.3	BMP t-score or z-score <-2.5	Pathological fracture	Pathological fracture causing life threatening consequences

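### Appendix 4 gives no numeric grade to a diastolic pressure above 110 or to a sodium of exactly 130

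*Protocol*

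**What the plan says.** Section 7.5.1.1 makes Appendix 4 the operative scale: "AE severity should be recorded and graded according to the Grading Scale". Section 7.6.1.1 applies the same scale to toxicity management. Section 8.3.2.1 says that the laboratory dataset will "re-grade the laboratory toxicity per protocol".

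In the hypertension row, Grade 1 is "Systolic: 140-159 Diastolic: 90-99" and Grade 2 is systolic 160-179, diastolic 100-109. Grade 3 is "Systolic: >179 Diastolic: 110". Grade 4 carries no pressure limit; it requires a life-threatening state or hospital admission.

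The sodium row reads "Hyponatremia >130 125-129 121-124 <121", from Grade 1 on the left to Grade 4 on the right.

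The grade has consequences in section 7.6. Grades 1 and 2 share one rule in 7.6.2: continuation at the investigator's discretion. For a Grade 3 event considered related, 7.6.3.2 states that "study drug will be withheld until the toxicity returns to" Grade 2 or lower.

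**The concern.** A grading scale that drives a rule should give every abnormal value exactly one grade. Here two values, or ranges of values, fall through.

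The diastolic gap matters more because it lies on the Grade 3 threshold, where withholding starts and from which release is judged. If the cell is applied as printed, a pressure that rises from 110 to a higher diastolic value leaves Grade 3. On paper that could satisfy the condition for restarting drug.

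The sodium gap lies between Grades 1 and 2. It matters for the laboratory re-grading step, which has no category for a result of 130.

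Blood pressure is one of the vitals listed in section 6.2.4.3.1, and Table 6.2.4.1.2 schedules vitals at every clinic visit. Section 6.2.4.1.2.1 lists a metabolic panel among the labs at each visit. Both rows will therefore be used.

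**Working it through.** **Inputs.** The cut-offs are those printed in Appendix 4. The number of subjects (30) is the target in section 6.2.2.1. The scheduled metabolic panels (baseline, Week 4, Week 16) are from Table 6.2.4.1.2.

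**Diastolic limits, applied one by one**

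| Diastolic | Grade by diastolic |
|---|---|
| 90, 99 | 1 |
| 100, 109 | 2 |
| 110 | 3 |
| 111, 115, 120, 130 | none, unless the clinical Grade 4 criterion is met |

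**Both limits together**, taking the higher grade where both apply and assuming no Grade 4 criterion is met

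| Pressure | By systolic | By diastolic | Result |
|---|---|---|---|
| 165/110 | 2 | 3 | 3 |
| 165/118 | 2 | none | 2 |
| 135/118 | none | none | none |
| 185/115 | 3 | none | 3 |

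Set beside 7.6.3.2: a related event at 165/110 is Grade 3, so drug is withheld until Grade 2 or lower. A later 165/118 is Grade 2 as printed, so the release condition is met although the diastolic pressure has risen by 8.

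**Sodium limits.** 129 gives Grade 2, 130 gives no grade, and 131 gives Grade 1. The row prints no upper end for Grade 1; I take it to stop at the laboratory's lower limit of normal, which does not affect the gap at 130.

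**How often sodium 130 might occur.** The protocol gives no sodium distribution, so this rests on assumed normal distributions with mean 138-140 and SD 2.5-3, rounded to whole numbers. P(130) = Φ((130.5 − mean)/SD) − Φ((129.5 − mean)/SD).

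- Mean 138, SD 3 (most frequent): Φ(−2.50) − Φ(−2.83) ≈ 0.0039.
- Mean 140, SD 2.5 (least frequent): Φ(−3.80) − Φ(−4.20) ≈ 0.00006.

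Scheduled results: 30 × 3 = 90. Expected results at 130: 90 × 0.0039 ≈ 0.35 at most and 90 × 0.00006 ≈ 0.005 at least.

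**The case against.** The bare 110 may be an inequality sign lost when the PDF was read. That is possible and must be checked against the original file. However, the sign before 179 survived in the same cell, and other inequality signs survived elsewhere in the appendix.

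The practical effect is also limited. Section 8.3.2.1 re-grades laboratory data only, so no program re-grades blood pressure under that section. An investigator grades it and may well not follow the cell literally. Section 7.6.3.2 applies only to events considered related. Sodium 130 cannot alter drug management, because 7.6.2 treats Grades 1 and 2 alike. All of this stands and keeps the point small. The protocol still fixes these cut-offs itself, so a separate analysis plan would not be expected to repair them.

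A reader might infer more than the document supports:

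- *That the diastolic limits grade a higher pressure lower than 110.* Above 110 they give no grade. A lower grade arises only where the systolic value supplies one.
- *That liver enzymes and BUN have similar holes*, at 2.5-2.6 and 5.0-5.1 times the upper limit of normal. Those limits adjoin at the one-decimal precision printed.
- *That mild symptoms cannot be graded.* Headache has a Grade 1 cell, "Minimal but detectable on exam, without impact on activities"; its wording is awkward, but the cell exists. Insomnia starts at Grade 2 ("Insomnia NA moderate, with impact on activities or part-time special resources indicated"), but NA at Grade 1 recurs in many rows and looks deliberate. The tolerability endpoint in 4.2.2.1 uses a patient questionnaire, not these grades.
- *That the sodium gap is large*, because under the same assumptions 130 would make up most results at or below 130. That is a share of a very small tail; the expected count is the relevant size.

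**Conclusion.** The point holds for two rows. As printed, a diastolic pressure of 111 or more has no diastolic grade, and a sodium of exactly 130 has no grade.

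The diastolic gap is the more important one because it conflicts with the Grade 3 withholding and release rule in 7.6.3.2. It depends on the cell being printed in the original as it appears here. The sodium gap affects laboratory grading only, with about 0.005 to 0.35 results expected over 90 scheduled panels under the assumed distributions.

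The primary endpoint and the sample size are not touched. Severity is minor.

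**What to change.** First, check the Grade 3 hypertension cell against the original protocol file. Then have the sponsor's clinicians reconcile the hypertension and hyponatremia rows so that neighbouring grades adjoin and every abnormal value has exactly one grade. Where the unassigned values fall is their decision; this review proposes no threshold. Check the revised rows against section 7.6, in particular the withholding and release condition in 7.6.3.2. Use the corrected table both for grading by investigators and for the laboratory re-grading in 8.3.2.1.

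The cost is an edit to two rows of one appendix table. It needs no new data and no extra visits.

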## APPENDIX 4: Grading Scale for Severity of Adverse Events and Laboratory Abnormalities

Pericardial effusion	Asymptomatic, small	Asymptomatic, mod-large	Physiologic consequences, no urgent intervention indicated	Physiologic consequences, urgent intervention indicated
PR prolongation	0.21-.025	>0.25	Type II 2 nd degree AV block	Complete AV block
Prolonged QTc	450-470 Or increase <30 above baseline	471-499 Or increase 30-50 above baseline	>499 Or increase >50 above baseline	Life threatening dysrhythmia
Thrombus	NA	DVT, no intervention or anticoagulation indicated	DVT, intervention or anticoagulation indicated	PE or life-threatening embolism
Vasovagal episode	No LOC	LOC	NA	NA
Ventricular dysfunction	NA	Asymptomatic and intervention indicated	New/worsening symptomatic CHF	Life threatening CHF
Bronchospasm	FEV1 70-80%	FEV1 50-69%	FEV1 25-49%	FEV1<25%, cyanosis or intubation
Dyspnea	On exertion, minimal, without impact on activities	On exertion, moderate, with impact on activities	At rest, unable to perform typical activities	Resp failure with vent support indicated
Uveitis	Asymptomatic	Symptomatic or intervention indicated	Posterior or pan-uveitis or operation indicated	Disabling visual loss
Visual changes from baseline	minimal, without impact on activities	moderate, with impact on activities	unable to perform typical activities	Disabling visual loss
Alopecia	Thinning detectable by subject	Thinning/patchy hair loss detectable by provider	Complete hair loss	NA
Rash	Localized macular rash	Diffuse rash or target lesions; no vesicles, bulla or ulceration. No mucosal involvement	Diffuse rash or target lesions; with vesicles, few bulla or superficial ulceration. mucosal involvement of one site	Extensive bullous lesions/more than one site of mucosal involvement, Stevens-Johnson syndrome or toxic epidermal necrolysis
Pigmentation changes	Slight or localized	Marked or generalized	NA	NA
Pruritis	minimal, without impact on activities	moderate, with impact on activities	Severe, unable to perform typical activities	NA
Anorexia	Mild, not decreasing intake	Decreased intake, no significant weight loss	Significant weight loss	Aggressive intervention indicated (i.e. feeding tube) or life threatening
Ascites	Asymptomatic	Symptomatic, Intervention indicated	Symptomatic despite intervention	Life threatening consequences

## APPENDIX 4: Grading Scale for Severity of Adverse Events and Laboratory Abnormalities

Cholecystitis	NA	Medical intervention indicated	Procedure indicated	Life threatening consequences (sepsis/perforation)
Constipation	NA	Persistent, requiring regular use of diet modification, laxatives/enemas	Obstipation with manual evacuation indicated	Life threatening consequences (obstruction)
Diarrhea	Transient/ intermittent or increase of >3 stools over baseline/24 hr.	Persistent or increase of 4-6 stools over baseline/24 hr.	Bloody diarrhea or increase of >6 stools over baseline/24 hr.	Life threatening consequences (shock)
Dysphagia	Able to eat usual diet	Causes alteration of diet, but no medical intervention indicated	Causes severe alteration of diet, medical intervention indicated	Life threatening reduction of oral intake
Mucositis/stomatitis	Erythema	Patchy Ulcerations or pseudomembranous	Confluent Ulcerations or pseudomembranous or mucosal bleeding	Tissue necrosis or diffuse mucosal bleeding or life threatening consequences
Nausea	Transient or intermittent	Persistent resulting in decreased oral intake 24-48 hours	Persistent resulting in minimal oral intake >48 hours or aggressive rehydration indicated	Life threatening consequences
Pancreatitis	NA	Symptomatic, no hospitalization indicated	Symptomatic, hospitalization indicated	Life threatening consequences
Proctitis	Discomfort	Minimal interference with usual activities or medical intervention indicated	Unable to perform usual activities or operative intervention indicated	Life threatening consequences
Vomiting	Transient or intermittent	Persistent resulting in decreased oral intake 24-48 hours	Persistent resulting in minimal oral intake >48 hours or aggressive rehydration indicated	Life threatening consequences
Psychiatric issues (i.e. anxiety, agitation, depression, mania, psychosis)	minimal, without impact on activities	moderate, with impact on activities	Severe, unable to perform typical activities	Behavior potentially harmful to self/others or unable to perform self-care
AMS	minimal, without impact on activities	lethargy, with impact on activities	Confusion, memory impairment lethargy, or somnolence, unable to perform typical activities	Delirium/obtundation or coma
Ataxia	Minimal but detectable on exam, without impact on activities	moderate, with impact on activities	marked, unable to perform typical activities	Disabling causing inability to care for self

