## APPENDIX 4: Grading Scale for Severity of Adverse Events and Laboratory Abnormalities

Osteonecrosis	NA	Asymptomatic but with radiologic findings and no surgical intervention indicated	symptomatic with radiologic findings or surgical intervention indicated	Disabling bone pain with radiologic findings causing inability to care for self
Acute systemic allergic reaction	Localized urticaria with no medical intervention indicated	Localized urticaria with mild angioedema with no medical intervention indicated	Gen urticaria or angioedema with medical intervention indicated or bronchospasm	Anaphylaxis, laryngeal angioedema, laryngeal edema or life-threatening bronchospasm
Chills	without impact on activities	moderate, with impact on activities	severe, unable to perform typical activities	NA
Fatigue/malaise	without impact on activities	moderate, with impact on activities	severe, unable to perform typical activities	Incapacitating symptoms, unable to perform basic self-care
Fever	99.8-101.5	101.6-102.8	102.9-104.9	>104.9
Pain	without impact on activities	moderate, with impact on activities	severe, unable to perform typical activities	Incapacitating symptoms, unable to perform basic self-care
Unintentional weight loss	NA	5-9% loss of body weight	10-19% loss of body weight	>19% loss of body weight or aggressive intervention indicated (feeding tube, TPN)
Lipodystrophy or lipoatrophy	detectable by subject	Detectable by provider	Obvious or disfiguring	NA
Diabetes mellitus (new onset)	NA	without indication for medications	Medications indicated	Life threatening consequences
Diabetes mellitus (existing)	NA	Requiring modification of medications	Lack of control despite medication modification	Life threatening consequences
Gynecomastia	detectable by subject	Detectable by provider	Obvious or disfiguring	NA
Hyperthyroidism	asymptomatic	Symptoms causing moderate impact of activities OR medication indicated	Symptoms causing inability to perform activities OR medication indicated	Life threatening consequences
Hypothyroidism	asymptomatic	Symptoms causing moderate impact of activities OR medication indicated	Symptoms causing inability to perform activities OR uncontrolled despite medication	Life threatening consequences
Intermenstrual bleeding	Spotting	≤ typical menstrual cycle	≥ typical menstrual cycle	Hemorrhage with life threatening hypotension

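### Several Appendix 4 severity cells are wrong as printed, most clearly diarrhea Grade 1 and hyperthyroidism Grades 2 and 3, and no rule says which grade applies when two fit

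*Protocol*

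**What the plan says.** Protocol 7.5.1.1 has adverse event severity graded by Appendix 4, and 7.6.1.1 repeats this for toxicity management. The grade then sets the drug action. At Grades 1 and 2, continuing is at the investigator's discretion (7.6.2.1). A Grade 3 event judged unrelated may be continued through (7.6.3.1). A related Grade 3 event means withholding until the toxicity is back to Grade 2 or lower, then restarting at full dose (7.6.3.2).

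The diarrhea row gives these stool counts:

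- Grade 1: "increase of >3 stools over baseline/24 hr", or transient/intermittent diarrhea
- Grade 2: "Persistent or increase of 4-6 stools over baseline/24 hr"
- Grade 3: "Bloody diarrhea or increase of >6 stools over baseline/24 hr"

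The hyperthyroidism row gives Grade 2 as "Symptoms causing moderate impact of activities OR medication indicated" and Grade 3 as "Symptoms causing inability to perform activities OR medication indicated". The hypothyroidism row directly below has the same Grade 2 wording, but its Grade 3 is "Symptoms causing inability to perform activities OR uncontrolled despite medication".

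Sections 7.5 and 7.6 and Appendices 3 and 4 contain no rule for an event that meets two grades. The nearest instruction, in 7.5.1.1, says that events associated with laboratory abnormalities are graded on clinical severity in context. It does not choose between two clinical cells.

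**The concern.** A severity scale that triggers withholding should put each event in one grade, or say how to choose. In the diarrhea row the mildest grade covers both higher count ranges. In the hyperthyroidism row one criterion appears on both sides of the line between discretion and mandatory withholding.

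Two things are at stake: the severity that is recorded, and the decision to stop and restart antiretroviral therapy. The restart test is blurred as well, because a subject with 7 extra stools already meets Grade 1 as printed. Diarrhea is one of the symptoms on the HIV Symptom Index (Appendix 2), so the row is likely to be used.

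**Working it through.** **1. Diarrhea, count criterion alone.** The inputs are the three printed limits: more than 3, 4 to 6, and more than 6.

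| Extra stools/24 hr | Grades met as printed | Grades met if Grade 1 is ≤3 |
|---|---|---|
| 1-3 | none | 1 |
| 4-6 | 1 and 2 | 2 |
| 7 or more | 1 and 3 | 3 |

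The 4-6 overlap does not change the drug action, since 7.6.2.1 covers both grades. The overlap at 7 or more does: Grade 1 is discretionary, and a related Grade 3 is withheld. Grades 2 and 3 run upward without a gap from 4, so an upper limit of 3 was evidently meant for Grade 1.

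**2. Diarrhea, whole row after that edit.** The non-count wording still overlaps:

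- transient bloody diarrhea with 1-3 extra stools fits Grades 1 and 3;
- persistent non-bloody diarrhea with 1-3 fits Grades 1 and 2;
- persistent non-bloody diarrhea with 7-8 fits Grades 2 and 3.

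Taking the highest grade met gives one grade in every combination. A highest-grade rule without the edit leaves 1-3 extra stools with no count-based grade.

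**3. Hyperthyroidism.** Let M be moderate impact, I be inability to perform activities, and T be medication indicated. Grade 2 is M or T, and Grade 3 is I or T. Every case with T meets both. A highest-grade rule alone makes every T case Grade 3, so the T clause in Grade 2 would never apply. A related case would then stay above Grade 2 for as long as medication was indicated, even with symptoms controlled. The row needs a distinct Grade 3 criterion, not only a tie-break.

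**4. Overlaps that a tie-break settles.** The QTc row combines absolute values with rises from baseline. Grade 1 is 450-470 or a rise under 30, Grade 2 is "471-499 Or increase 30-50 above baseline", and Grade 3 is ">499 Or increase >50 above baseline".

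- 400 to 455 is a rise of 55: Grade 1 by value, Grade 3 by rise.
- 420 to 475 is a rise of 55: Grade 2 by value, Grade 3 by rise.
- 430 to 465 is a rise of 35: Grade 1 by value, Grade 2 by rise.

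Sodium of 154 and bilirubin of 2.5 × ULN each sit in two adjacent grades, and the infection row overlaps through its wording. Such overlaps are ordinary if the highest grade is used, but the protocol does not say so.

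**5. Errors that a tie-break cannot settle.**

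- PR prolongation Grade 1 is printed as 0.21 to .025, which runs backwards. Grade 2 starts above 0.25, so 0.25 was evidently meant.
- Hyponatremia Grade 1 is above 130 and Grade 2 is 125-129, so a sodium of 130 has no grade.
- Hypertension Grade 2 diastolic ends at 109 and Grade 3 is exactly 110. A diastolic pressure of 111 or more therefore meets no Grade 1 to 3 diastolic value; ≥110 was evidently meant.

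**6. Endpoint rows.** For the endpoint in 4.2.2.3, creatinine (1.5-2.0, 2.01-3.00, 3.01-6.00, >6.00) and AST/ALT (1.25-2.5, 2.6-5.0, 5.1-10, >10 × ULN) share no values between grades.

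**The case against.** The best defence is that these are editorial slips with little consequence. Withholding at a related Grade 3 is mandatory, and 7 or more extra stools expressly meets the Grade 3 cell, so going wrong requires a grader who stops at the first cell. The investigator or a qualified sub-investigator confirms the accuracy of assessments (7.3.1.1), toxicity questions go to the investigator (7.6.1.3), and recruitment is at a single site, so inconsistent grading is unlikely. No thyroid test is scheduled, so hyperthyroidism would surface only clinically. This stands and limits the size of the point. It does not make the cells correct or supply a rule.

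It can also be said that other Grade 1 cells are open-ended, such as hyponatremia above 130 or hypokalemia above 3. Those are open towards normal, where the normal range closes them. The diarrhea cell is open towards greater severity, which a sensible reading of one cell does not close.

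A reader might infer that mild diarrhea cannot be graded at all. The documents do not support that: 1-3 extra stools can still be graded as transient (Grade 1) or persistent (Grade 2).

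The > sign could be an artefact of text conversion. That cannot be excluded, but ≤ survives elsewhere in the same appendix (the hemorrhage and intermenstrual bleeding rows), so > is probably as printed. If it is not, the other parts of the point remain.

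**Conclusion.** The point holds as a correction to consider. Diarrhea Grade 1 and the hyperthyroidism row are wrong as printed, three other cells contain errors that a tie-break would not repair, and no rule covers overlapping grades. These cells belong to a scale that investigators use at visits to decide on withholding, so this is protocol content and not something to leave to a statistical analysis plan.

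The practical effect is small. The protocol gives no event rates; with 30 subjects followed for 16 weeks, few affected cases are to be expected.

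Two stronger readings are tempting. One is that subjects with severe diarrhea would be kept on drug; the whole row leads to Grade 3, so the text does not support this. The other is that trial results are at risk. The adherence endpoint does not use the scale, and the HIV Symptom Index asks how much a symptom bothers the subject, not stool counts. The creatinine, AST and ALT rows have no overlapping grades. No efficacy or laboratory endpoint depends on the diarrhea or hyperthyroidism rows.

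**What to change.** 1. Diarrhea Grade 1: change the count to *increase of ≤3 stools over baseline/24 hr.*
2. Hyperthyroidism Grade 3: replace the shared medication clause with a distinct one, for example the hypothyroidism model, "Symptoms causing inability to perform activities OR uncontrolled despite medication". The investigator should confirm this, because it raises the threshold for withholding: hyperthyroidism controlled on medication would become Grade 2.
3. Add to 7.5.1.1, and state that it applies also to 7.6.1.1: *If more than one grade fits, the highest applicable grade is assigned.* Keep the existing clinical-severity rule for laboratory-associated events. The sentence belongs in 7.5.1.1 because that section governs recorded severity; placed only under toxicity management, it would miss half of the problem.
4. In the same edit, change the PR prolongation Grade 1 upper limit to 0.25, assign sodium of 130 to a grade (Grade 1 as ≥130 would do), and change the Grade 3 diastolic value to ≥110.

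The cost is five cells and one sentence with a cross-reference, submitted to the IRB as a protocol modification under 9.14.1. It adds no visits, procedures or data.
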